3.3.3 Exclusion criteria

1. Prior erlotinib, gefitinib or lapatinib therapy or prior exposure to any investigational EGFR or panErbB reversible or irreversible inhibitor or any prior panitumumab or investigational EGFR-directed monoclonal antibody. Cetuximab is permitted if used for locally advanced disease, as long as no disease progression within 6 months. Cetuximab use is not permitted for recurrent/metastatic disease.

2. Radiotherapy within 2 weeks prior to enrollment. Palliative radiation to target organs may be allowed up to 2 weeks prior to enrollment, as long as there are other target lesions that can be monitored for response to study treatment.
3. Known hypersensitivity to afatinib or its excipients
4. Women of child-bearing potential (WOCBP) and men who are able to father a child, unwilling to be abstinent or use highly effective methods of birth control prior to study entry, for the duration of study participation and for at least 4 weeks after treatment has ended.
5. Pregnant or nursing women.
6. Any history of or concomitant condition that, in the opinion of the Investigator, would compromise the patient's ability to comply with the study or interfere with the evaluation of the efficacy and safety of the test drug.
7. Concomitant malignancies at other sites that are being actively treated with systemic therapy
8. Requiring treatment with any of the prohibited concomitant medications listed in Section 4.2.2.1 that cannot be stopped for the duration of trial participation.
9. Clinically significant interstitial lung disease.
10. Known history of untreated viral hepatitis or HIV.
11. Patients with parenchymal brain metastases are not eligible, unless they have completed local therapy.
12. Leptomeningeal carcinomatosis.

3.3.4 Removal of patients from therapy or assessments

Patients may discontinue study treatment at any time. Any patient who discontinues treatment will be encouraged to return to the study center to undergo treatment discontinuation assessments and to receive supportive care as indicated. We will permit progression and survival data collection unless the patient specifically withdraws consent for data collection for

the trial. The primary reason for discontinuation should be recorded. Reasons for discontinuation of a patient by the investigator include, but are not limited to, the following:

- Documented disease progression
- Intolerable side effects, defined as grade 3 or higher drug related toxicity that fails to resolve to Grade 2 despite appropriate supportive care
- Clinically significant deterioration of the patient's condition causing a change in performance status prior to treatment discontinuation
- Patient noncompliance
- Investigator determination that it is not in the patient's best interest to continue participation
- Pregnancy
- Patient withdrawal of consent

4. TREATMENTS

4.1 TREATMENTS TO BE ADMINISTERED

4.1.1 Identity of Investigational Product

Substance (INN)	Afatinib
(Brand name):	GIOTRIF®/GILOTTRIF®
Pharmaceutical form:	Film-coated tablet
Source:	Boehringer Ingelheim Pharma GmbH & Co. KG
Unit strength:	20 and 30 mg film-coated tablets (the dose of afatinib in the film-coated tablets is related to the free base equivalent to afatinib)
Route of administration:	Oral
Posology	Once daily

4.1.2 Standard therapy: Cetuximab

Brand Name:	Erbitux
Pharmaceutical form:	Injection for intravenous infusion
Source:	to be covered by patient's insurance carrier
Unit strength:	400mg/m ² body surface area loading dose, followed by 250 mg/m ² body surface area weekly thereafter
	OR
	500mg/m ² body surface area initial dose and bi-weekly thereafter
Route of administration:	Intravenous injection
Posology:	Weekly/Bi-weekly
Premedications:	May premedicate with an H1 antagonist (eg, 50 mg of diphenhydramine) intravenously and steroid (dexamethasone 10 mg oral/intravenous) 30–60 minutes prior to the first dose. It is also

recommended to give a dose of dexamethasone 8 mg PO approximately 12 hours before the first and second scheduled cetuximab infusions. Premedication should be administered for subsequent cetuximab doses based upon clinical judgment and presence/severity of prior infusion reactions.

4.1.2 Method of assigning patients to treatment groups

Since this is an open-label, single-arm study, all enrolled patients will receive the combination of Cetuximab (standard therapy covered by patient's insurance carrier) and Afatinib (provided by Boehringer Ingelheim).

4.1.3 Selection of doses in the trial

Cetuximab at the proposed doses is FDA approved for the treatment of metastatic SCCHN. In the Phase I open-label dose-escalation study, the MTD of Afatinib was determined to be 40mg [14]. This dose has been tested in several Phase II and III trials as outlined in Section 1 above and found to be safe and effective. Afatinib 40 mg was also tested in combination with Cetuximab in patients with lung cancer who harbor the EGFR mutation and was shown to have a manageable side effect profile with not disproportionate treatment related mortality [22]. This was the dose initially used for patients accrued to the study, however, most patients needed a dose reduction to 30 mg daily. We will start all subsequent patients on this trial at a 30 mg daily dose.

4.1.4 Drug assignment and administration of doses for each patient

4.1.4.1 Administration of afatinib

Patients will take a single oral dose of afatinib each day starting at a dose of 30 mg, continuously, until the development of progressive disease or unacceptable adverse events. Dose reductions of afatinib can occur. See Sections 4.1.4.1.1 and 4.1.4.1.2.

The medication should be taken at approximately the same time each day without food (at least one hour before or at least three hours after a meal).

Missed doses of afatinib can be made up during the same day as soon as the patient remembers. However, if the next scheduled dose is due within 8 hours then the missed dose must be skipped. Patients with emesis must not take a replacement dose.

If dosing of whole tablets is not possible, afatinib tablets can also be dispersed in approximately 100 ml of non-carbonated drinking water. No other liquids should be used. The tablet should be dropped in the water, without crushing it, and occasionally stirred for up to 15 min until the tablet is broken up into very small particles. The dispersion should be drunk immediately. The glass should be rinsed with approximately 100 ml of water which should also be drunk. The dispersion can also be administered through a naso-gastric tube or enteral feeding tube.

Medication will be dispensed in bottles containing 30 tablets at the beginning of each treatment cycle. For administrative purposes, a treatment cycle is defined as 28 (+/- 3) days. Treatment will start after baseline evaluations and stop when the patient is diagnosed with disease progression or for any reason detailed in Section 3.3.4. Study drug will be prescribed by the investigator and will be dispensed by the affiliated investigational pharmacy on day 1 of each cycle.

4.1.4.1.1 Dose escalation for afatinib

Afatinib dose will not be escalated beyond the 30 mg daily oral dose on this trial.

4.1.4.1.2 Dose reduction for afatinib

Treatment related AEs will be managed by treatment interruptions and subsequent dose reductions of afatinib according to the schedule described in Table 4.1.4.1.2: 1. Given overlapping toxicities, afatinib dose reductions should precede cetuximab dose reductions. Dose reductions will apply to individual patients only. Once the dose has been reduced, it cannot be increased later.

To prevent the development of more severe adverse events, treatment related diarrhea or rash should be managed early and proactively as described in Section 4.2.3.

Table 4.1.4.1.2: 1 Dose reduction scheme for afatinib

AE type and CTCAE Grade	Action	Dose reduction scheme
Events related to study drug: 
 Diarrhea Grade 2 persisting for 2 or more consecutive days (48 hours) despite adequate anti-diarrheal medication/hydration Reduced renal function to \geq Grade 2 as measured by serum creatinine, proteinuria or decrease in glomerular filtration rate of more than 50% from baseline Any other drug related AE Grade \geq3 	Pause treatment until patient has recovered to Grade \leq 2 (Grade \leq 1 for diarrhea or impaired renal function only) or baseline ¹ . Resume treatment at reduced dose according to schedule opposite. If patient has not recovered to Grade \leq 2 (Grade \leq 1 for diarrhea or impaired renal function) or baseline ¹ within 14 days, study treatment	If patient was receiving Afatinib 30 mg daily, resume treatment at a dose of 20 mg daily. If patient was receiving Afatinib 20 mg daily, resume treatment at 20 mg intermittent dosing, 5 days on, 2 days off. If patient was receiving Afatinib 20 mg intermittent dosing, discontinue treatment.

AE type and CTCAE Grade	Action	Dose reduction scheme
	must be permanently discontinued ² .	
Acute onset and/or unexplained worsening of pulmonary systems (dyspnoea, cough, fever)	Pause afatinib while clinical assessment to exclude ILD is completed.	If ILD is ruled out as a cause of symptoms, grade symptoms and relatedness and report as AEs. If AEs are not related, resume afatinib at current dose. If AEs are drug related, follow directions in row above. If ILD is confirmed, discontinue afatinib

¹ Baseline is defined as the CTCAE Grade at the start of treatment

² In the event that the patient is deriving obvious clinical benefit according to the investigator's judgement, further treatment with afatinib will be decided in agreement between the sponsor and the investigator.

In the event of any unrelated adverse events, the investigator may choose to interrupt the medication for up to 14 days, but no dose reduction should occur. If the medication is interrupted for more than 14 days, the decision to continue with afatinib will be made by the sponsor in agreement with the investigator.

4.1.4.2 Administration of Cetuximab

Pre-medication with dexamethasone 8 mg po or by feeding tube approximately 12 hours prior to cetuximab dosing for the first and second doses. This may be omitted if there is a relative contraindication (eg. poorly controlled diabetes or hypertension), and may be stopped after the second dose of cetuximab if no hypersensitivity is observed. Use of IV dexamethasone premedication on the treatment day is recommended.

30-60 minutes after the recommended pre-medications per treating physician discretion, cetuximab will be administered intravenously at a dose of 400mg/m² on cycle 1, day 1 of treatment (loading dose) and at a dose of 250mg/m² every 7 days (+/- 1 day) thereafter. Alternatively, patients can be treated at a dose of 500mg/m² every 14 days (+/- 2 days). Alternating Cetuximab dosing schedules from a weekly to bi-weekly dosing schedule, and vice versa, between and within cycles of treatment is permitted per protocol following Sponsor PI discussion and approval.

Do not administer cetuximab as an intravenous push or bolus.

Administer via infusion pump or syringe pump. Do not exceed an infusion rate of 10 mg/min.

Administer through a low protein binding 0.22-micrometer in-line filter.

Parenteral drug products should be inspected visually for particulate matter and discoloration prior to administration, whenever solution and container permit.

The solution should be clear and colorless and may contain a small amount of easily visible, white, amorphous, cetuximab particulates. **Do not shake or dilute.**

4.1.4.2.1 Dose escalation for cetuximab

Cetuximab dose beyond the recommended and approved dosing will not be escalated on this trial.

4.1.4.2.2 Dose reduction for cetuximab

Infusion Reactions

Reduce the infusion rate by 50% for NCI CTC Grade 1 or 2 and non-serious NCI CTC Grade 3 infusion reaction.

Immediately and permanently discontinue Erbitux for serious infusion reactions. Afatinib may be continued by itself at the discretion of the treating physician, in patients who have experienced a serious infusion reaction with cetuximab.

Dermatologic Toxicity

Recommended dose modifications for severe (NCI CTC Grade 3 or 4) acneiform rash are specified in Table 4.1.4.2.2: 1 below. Afatininib should be dose reduced first per the guidelines in Table 4.1.4.1.2 above, before dose reducing cetuximab.

Table 4.1.4.2.2: 1 Cetuximab Dose Modification Guidelines for Rash

Grade 3/4 Acneiform Rash	Erbitux	Outcome	Dose Modification
1 st occurrence	Delay infusion 1 to 2 weeks	Improvement No Improvement	Continue at 250 mg/m ² (500mg/m ² for bi-weekly dosing)

			Discontinue Erbitux
2 nd occurrence	Delay infusion 1 to 2 weeks	Improvement	Reduce dose to 200mg/m ² (400mg/m ² for bi-weekly dosing)
		No Improvement	Discontinue Erbitux
3 rd occurrence	Delay infusion 1 to 2 weeks	Improvement	Reduce dose to 150mg/m ² (300mg/m ² for bi-weekly dosing)
		No Improvement	Discontinue Erbitux
4 th occurrence	Discontinue Erbitux		

In the event of any adverse event, the treating physician may choose to interrupt cetuximab for up to 14 days. Treatment can then be resumed at the same or lower dose level. If the medication is interrupted for more than 14 days, the decision to continue with cetuximab will be made by the sponsor in agreement with the investigator.

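### For Grade 3/4 acneiform rash, the cetuximab table restarts on an ungraded improvement while Sections 3.1, 3.3.4 and the afatinib table look for recovery to Grade 2, and no precedence is stated

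*Combined protocol and SAP*

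**What the plan says.** Four places in the protocol bear on the same event, a drug-related acneiform rash of Grade 3 or 4.

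- **Section 4.1.4.2.2 (cetuximab).** The section states "Recommended dose modifications for severe (NCI CTC Grade 3 or 4) acneiform rash are specified in Table 4.1.4.2.2: 1 below". The table takes Grades 3 and 4 together. At each of the first three occurrences the action is "Delay infusion 1 to 2 weeks", and the outcome column then has two entries, extracted for the first row as "Improvement No Improvement". Neither is defined and neither carries a grade. For improvement after the first occurrence the entry is "Continue at 250 mg/m"² (500 mg/m² on the bi-weekly schedule), the unreduced dose. After the second and third occurrences the weekly dose falls to 200 and 150 mg/m² (400 and 300 mg/m² bi-weekly). A closing paragraph lets the physician interrupt cetuximab for up to 14 days for any adverse event and adds "Treatment can then be resumed at the same or lower dose level", again with no recovery grade.
- **Section 4.1.4.1.2 (afatinib).** Grade 3/4 rash falls under the row for other drug-related events of Grade 3 or higher. Afatinib is paused until Grade 2 or less, or baseline. If that is not reached within 14 days, study treatment is to stop permanently. Footnote 2 leaves further afatinib to the sponsor and investigator when there is obvious clinical benefit. On the last dose level the instruction is "If patient was receiving Afatinib 20 mg intermittent dosing, discontinue treatment".
- **Section 3.3.4.** Intolerable side effects are a reason for discontinuation, "defined as grade 3 or higher drug related toxicity that fails to resolve to Grade 2" despite supportive care.
- **Section 3.1.** The same threshold appears as a statement that treatment will be discontinued. The synopsis repeats it.

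**The concern.** The cetuximab table uses a grade to let a patient in (3 or 4) but none to let the patient restart. The other three places all use Grade 2 as the dividing line. Where a rash has become less severe but is still above Grade 2, the sections can give opposite instructions, and no sentence says which one prevails.

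This is first a safety matter: one compliant investigator could give the next infusion and another could stop, for the same rash on the same drugs. It also reaches the secondary objective on safety and tolerability. Discontinuations and cetuximab dose intensity would partly reflect which section a site followed. Skin toxicity is not a remote case here: Section 4.2.3 names dermatologic events and diarrhea as the most common side effects of afatinib, and 4.1.4.1.2 acknowledges that the two drugs have overlapping toxicities.

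**Working it through.** There is no planned figure to reproduce and no sample size, power or error rate involved. The check sets the rules side by side for defined cases.

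**Case A.** First occurrence, drug-related rash, Grade 4 at onset, Grade 3 on day 14, baseline skin grade 2 or less, both drugs held from the same day.

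| Rule | Test applied | Time limit | Result for Case A |
|---|---|---|---|
| 4.1.4.2.2, rash table | improvement, no grade | 1 to 2 weeks (7 to 14 days) | literally met; cetuximab resumes unreduced |
| 4.1.4.2.2, closing paragraph | none | up to 14 days | resumption at the same or a lower dose allowed |
| 4.1.4.1.2, afatinib table | Grade 2 or less, or baseline | 14 days | not met; study treatment stops unless footnote 2 is used |
| 3.1 | failure to resolve to Grade 2 | none | Grade 2 not reached; stops once supportive care is judged to have failed |
| 3.3.4 | same | none | same; listed reason for discontinuation |

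1. Grade 3 is less severe than Grade 4, so the first row is satisfied on its ordinary meaning.
2. Grade 3 is above Grade 2, so the afatinib table's test is failed at day 14 and the level set in 3.1 and 3.3.4 has not been reached.
3. No section ranks these rules, so the text permits both an infusion and a stop.
4. At a second or third occurrence the difference in recovery test is the same, but the table's restart dose is then a reduced one. Restart at the unreduced dose is therefore specific to the first occurrence and to the closing paragraph.

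**Case B.** Three separate drug-related Grade 3 rashes, each recovering to Grade 2 or less within 14 days, starting at afatinib 30 mg with no other dose reductions. The Grade 2 threshold is met every time, so the conflict in Case A does not arise.

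| Occurrence | Afatinib table | Cetuximab table, weekly schedule |
|---|---|---|
| 1 | 30 mg to 20 mg daily | 250 mg/m², unchanged |
| 2 | 20 mg daily to 20 mg, 5 days on and 2 off | 200 mg/m² |
| 3 | discontinue treatment | 150 mg/m² |

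At occurrence 3 the outcome turns on the word treatment. If it means afatinib, the patient continues on cetuximab alone, as the cetuximab table provides. If it means both drugs, the cetuximab table's instruction to go on cannot be followed.

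**Which meaning is more natural.** For afatinib alone: the table is titled and placed as an afatinib scheme, its footnote 2 speaks of further afatinib, and the note to the diarrhea table in 4.2.3.1 states the same 14-day stop for afatinib by name. For both drugs: the interstitial lung disease row of the same table names afatinib when it means afatinib, whereas the row covering rash does not. The protocol also provides expressly for afatinib alone after cetuximab stops (flow chart note k, 4.1.4.2.2, 6.2.2) but has no matching provision for cetuximab alone. Afatinib alone is the better reading, but the text does not settle it.

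**The case against.** The strongest defence is that the rules can be layered. The cetuximab table is labelled as guidelines and introduced as recommended, while 3.1 is worded as mandatory, so a general stop can sit above drug-specific dosing advice. Numbering the rows by occurrence of Grade 3/4 rash also suggests that one occurrence ends, below Grade 3, before the next begins. Both points are fair. Neither is written down: there is no precedence sentence, improvement is not tied to a grade, and the closing paragraph on any adverse event has no recovery test at all. An afatinib-only reading of the afatinib table removes its conflict with the cetuximab table but leaves the one with 3.1 and 3.3.4.

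Some stronger readings are tempting and are not supported.

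- *Any improvement suffices.* The table does not say any. The defect is an undefined term, which permits that reading without requiring it.
- *All the other rules stop treatment on the day cetuximab restarts.* Only the afatinib table has a 14-day limit, and footnote 2 qualifies it. Sections 3.1 and 3.3.4 set no day.
- *The tables break the afatinib-first rule.* The text says "afatinib dose reductions should precede cetuximab dose reductions". Case B satisfies this: afatinib falls at occurrence 1 and cetuximab first falls at occurrence 2. Nothing requires every afatinib level to be used up first.
- *The later cetuximab rows can never be reached.* This needs the both-drugs reading, which is the weaker one.
- *A percentage loss of dose measures the problem.* Such figures would describe one hypothetical sequence, not an expected effect. The base also matters: 150 mg/m² is 150/250 = 60% of the weekly maintenance dose, but the weekly schedule starts with a 400 mg/m² loading dose.

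**Conclusion.** The point stands as an internal inconsistency with a bearing on patient safety. For a Grade 4 rash that has lessened to Grade 3, the literal text meets the cetuximab restart condition and misses the Grade 2 threshold used in 3.1, 3.3.4 and the afatinib table, with no order of precedence. Separately, the unnamed object of the stop in the afatinib table leaves open whether cetuximab may continue at a third occurrence.

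The conclusion rests on the ordinary meaning of improvement, on the rash being drug related, and on a baseline grade of 2 or less. A rash that has shrunk but was Grade 3 throughout is a less clear instance, since it depends on whether change within a grade counts. The size cannot be put in numbers, because the documents give no frequency for Grade 3/4 rash on the combination. The primary response-rate test and the sample size are not affected; tolerability, discontinuation and dose-intensity summaries could be. The change should be made, and it is a matter of clarifying and aligning text.

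**What to change.** The sponsor should reconcile Sections 3.1, 3.3.4, 4.1.4.1.2 (including footnote 2) and 4.1.4.2.2 (table and closing paragraph) so that a single restart and stop criterion applies to the same rash, or so that the order of precedence is explicit. The amended text should say which drug or drugs study treatment and treatment refer to in the afatinib table. One table with a row per rash occurrence and a column for each drug would do both. Which of the existing rules or doses should stand is for the sponsor to decide; none is proposed here.

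The cost is one merged table in a protocol amendment and a memo to site staff. It needs no new procedures, visits or patients.

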4.1.5 Blinding and procedures for unblinding

4.1.5.1 Blinding

This is a single-arm, open-label study and will not employ randomization to assign treatment. All enrolled patients will receive the planned study treatment.

4.1.5.2 Procedures for emergency unblinding

This is a single-arm, open-label study and will not employ randomization to assign treatment. All enrolled patients will receive the planned study treatment.

4.1.6 Packaging, labelling, and re-supply

Afatinib will be supplied as film-coated tablets. Available dosage strengths will be 20 and 30 mg. Tablets will be supplied in HDPE, child-resistant, tamper-evident bottles.

Bottles/boxes will be labelled according to local regulations and will include the following as a minimum;

- Study number
- Product name (Afatinib)
- Contents of the bottle (30 tablets)
- Tablet strength (mg)
- Batch number
- Medication number
- Use-by date
- Storage information
- Instructions for use
- Sponsor name and address
- A statement that the medication is for clinical study use only
- A caution statement

Erbitux (cetuximab) is supplied at a concentration of 2 mg/mL as a 100 mg/50 mL, single-use vial or as a 200 mg/100 mL, single-use vial as a sterile, injectable liquid containing no preservatives.

NDC 66733-948-23 100 mg/50 mL, single-use vial, individually packaged in a carton

NDC 66733-958-23 200 mg/100 mL, single-use vial, individually packaged in a carton

